10.7 Continuous Monitoring Rule for Futility

The study will include a continuous Bayesian monitoring rule for futility. We will accrue and observe the first 8 evaluable patients on each arm, then continuously observe the proportion of patients who are without progression at 16-weeks. Based on the hypothesized increase in median progression-free survival from the historical rate of 2 months to 3.33 months in either the ficlatuzumab arm or the ficlatuzumab plus cetuximab arm, the expected proportion

progression-free at 16 weeks would be 0.46 under the alternative hypothesis. A Bayesian predictive probability design was used to estimate the rejection regions to stop an arm for futility.⁵² The rejection regions to stop an arm for futility are: 0/8, 1/9, 2/13, 3/16, 4/19, 5/21, 6/24, 7/26, 8/28, 9/29, 10/31, 11/32, 12/33. Thus, if none of the first 8 patients is progression-free at 16 weeks, that arm will be stopped, or if only 1 of the first 9 patients is progression-free, that arm will be stopped, etc. This design has 80% power at $\alpha = 0.10$ with an expected sample size of 21.3 under the null hypothesis and 31.4 under the alternative hypothesis. The probability of early termination under the null hypothesis is 0.86. The rejection regions were derived to maximize power under the alternative hypothesis. There was no Bayesian predictive probability design with 90% statistical power given the proposed median survival times and sample size with $\alpha = 0.10$.

11. DATA SAFETY MONITORING PLAN

11.1 Identification of the DSMB obligated for oversight responsibilities

[name] at the University of Arizona Cancer Center (UACC) will assume the role of the Sponsor. The UACC Data and Safety Monitoring Board (DSMB) will assume responsibility for oversight of safety monitoring. Based on the UACC DSMB Charter this is a high risk study.

11.2 Identification of the entity obligated and requirements for routine monitoring duties

Affiliate sites that participate in this trial will choose, through a reciprocal agreement with UACC, either to:

- 1) Perform monitoring per the sites' Data and Safety Monitoring Plan, only if the site has fully approved NCI Data and Safety Monitoring Plan.
- 2) Allow UACC to conduct remote and on-site monitoring for this trial in accordance with the UACC's approved NCI Data and Safety Monitoring Charter/Monitoring Plan.
- 3) Perform monitoring per the UACC's Data and Safety Monitoring Charter/Plan.

If a site-specific monitoring plan will be used, the UACC DSMB must review the sites' Data and Safety Monitoring Plan and approve that the plan is acceptable. If the UACC DSMB finds that a plan is not acceptable, the UACC or the site's internal monitors will perform monitoring per the UACC Data and Safety Monitoring Plan.

Elements that are required to be included within each site-specific DSM plan are:

- A process to verify eligibility by the local monitoring team.
- Frequency and extent of monitoring activities for this trial at the site

11.3 Monitoring progress, assuring data accuracy and protocol compliance

Frequency and methodology of routine monitoring may vary slightly from institution to institution.

Regardless of monitoring entity, all monitoring reports must be completed and submitted to the local site PI, the Sponsor-Investigator, and UACC DSMB.

All submitted serious adverse events will be submitted to the UACC DSMB Coordinator monthly and then reviewed by the DSMB Chair.

Any identified SAE trends will be made available for review at the investigator teleconferences.

A teleconference will occur on a regular schedule to review study progress and any safety, or other, issues. Minutes of these teleconference meetings will be submitted to UACC DSMB for review.

At each site, the Principal Investigator will ensure the accuracy, completeness, legibility and timeliness of the data reported in the OnCore electronic Case Report Form (eCRF), and other data formats. Source documentation supporting the study data should indicate the subject's participation in the trial and should document the dates and details of study procedures, adverse events, and patient status.

Case report forms, which include adverse event forms, serious adverse event forms, and protocol or patient deviations must be completed via the UACC OnCore CRM database.

11.4 Oversight Activities by the UACC DSMB

Any identified safety issue will be submitted to the UA IRB, DSMB or other oversight entity as applicable. In addition to review of site specific monitoring, the convened UACC DSMB will review all monitoring reports and findings every 6 months. Every 6 months, the UACC convened DSMB will perform a review of all study data which will include the following:

- SAEs
- AEs
- Protocol Deviations
- Any pending action items (i.e., responses to DSMB reports; pending items from routine monitoring reports).

Study activity and safety information will be routinely submitted to the UACC DSMB.

In addition to site specific monitoring, the local PI will complete a status report for each UACC DSMB review. These reports should include summaries of:

- Study activity, cumulative and for the period under review;
- Safety information (non-serious and serious adverse events);
- Status of study in relationship to stopping rules;
- Routine monitoring and protocol compliance (describe the monitoring process and identify the status of the monitoring);
- Attachments (AE data reviewed by the PI to compile the report, SAE reports, results of any review(s), applicable correspondence with the IRB or other regulatory agencies.

Data and Safety Monitoring Board determinations will be reported to the University of Arizona IRB at least annually. DSMB determinations will be distributed to the sites contemporaneously.

11.5 Process to implement study closure when significant risks or benefits are identified

This study may be prematurely terminated, if in the opinion of the investigator or Aveo, there is sufficient reasonable cause. Written notification documenting the reason for study termination will be provided to the investigator or Aveo by the terminating party.

Circumstances that may warrant termination include, but are not limited to:

- Determination of unexpected, significant, or unacceptable risk to patients
- Failure to enter patients at an acceptable rate
- Insufficient adherence to protocol requirements
- Insufficient complete and/or evaluable data
- Plans to modify, suspend or discontinue the development of the drug

Should the study be closed prematurely, remaining study drug must be returned to Aveo or destroyed.

11.6 Identification of the sponsor or funding agency, as applicable

[name] is the sponsor-investigator responsible for all requirements as set out in 21 CFR 312. Aveo Oncology provides support for the trial by providing the investigational product.

Page 61 of 76 v10, 05/23/2023

The sponsor-investigator will immediately notify applicable entities of any action resulting in a temporary or permanent suspension of the study.

12.ADVERSE EVENT REPORTING

12.1 Definitions

The following definitions of terms apply to this section:

Adverse event: Any untoward medical occurrence associated with the use of a drug in humans, whether or not considered drug related. The term "Adverse Event" is inclusive of SAEs.

Life-threatening adverse event or life-threatening suspected adverse reaction: An adverse event or suspected adverse reaction is considered "life-threatening" if, in the view of either the investigator or sponsor, its occurrence places the patient or subject at immediate risk of death. It does not include an adverse event or suspected adverse reaction that, had it occurred in a more severe form, might have caused death.

Serious adverse event: An adverse event is considered "serious" if it results in any of the following outcomes:

- death,
- a life-threatening adverse event,
- inpatient hospitalization or prolongation of existing hospitalization,
- a persistent or significant incapacity or substantial disruption of the ability to conduct normal life functions, or
- a congenital anomaly/birth defect.
- Important medical events that may not result in death, be life-threatening, or require
 hospitalization may be considered serious when, based upon appropriate medical
 judgment, they may jeopardize the patient or subject and may require medical or
 surgical intervention to prevent one of the outcomes listed in this definition.
- Pregnancy

Suspected adverse reaction: Any adverse event for which there is a reasonable possibility that the drug caused the adverse event. For the purposes of IND safety reporting, "reasonable possibility" means there is evidence to suggest a causal relationship between the drug and the adverse event. Suspected adverse reaction implies a lesser degree of certainty about causality than adverse reaction, which means any adverse event caused by a drug.

Unexpected adverse event or unexpected suspected adverse reaction: An adverse event or suspected adverse reaction is considered "unexpected" if it is not listed in the investigator brochure or is not listed at the specificity or severity that has been observed; or, if an

investigator brochure is not required or available, is not consistent with the risk information described in the general investigational plan or elsewhere in the current application, as amended. For example, under this definition, hepatic necrosis would be unexpected (by virtue of greater severity) if the investigator brochure referred only to elevated hepatic enzymes or hepatitis. Similarly, cerebral thromboembolism and cerebral vasculitis would be unexpected (by virtue of greater specificity) if the investigator brochure listed only cerebral vascular accidents. "Unexpected," as used in this definition, also refers to adverse events or suspected adverse reactions that are mentioned in the investigator brochure as occurring with a class of drugs or as anticipated from the pharmacological properties of the drug, but are not specifically mentioned as occurring with the particular drug under investigation.

12.2 Description of Adverse Event Reporting Procedures

Adverse events will be recorded in the adverse events record form in the UACC OnCore CRM and reviewed by the local Principal Investigator. All Adverse Events as defined in this section will be collected starting on Cycle 1, Day 1 must be recorded. AEs will be followed per the details indicated in protocol Section 8.5.1. Only AEs meeting one of the following criteria will be entered into the OnCore CRM study database:

- Any AE that is Grade 3 or higher, regardless of relationship to the study drug
- Any AE that results in submission of a Serious Adverse Event (i.e., hospitalization for a non-serious grade AE)
- Any intolerable (per the opinion of the treating investigator) Grade 2 AE
- Any Grade AE resulting in a dose reduction of ficlatuzumab or cetuximab
- Any Grade 2 laboratory or vital sign values that are deemed clinically significant by the treating investigator
- Any Grade AE in the following categories of interest:
 - o Rash
 - Diarrhea
 - o Edema, peripheral
 - o Edema, head, face and neck
 - o Hypoalbuminemia

All adverse events will be classified using either the MedDRA term or NCI Common Terminology Criteria for Adverse Events (CTCAE) version 4.0 and will address:

- Grade
- Relationship to ficiatuzumab (not related, unlikely, possible, probable, definitely)
- Relationship to cetuximab (not related, unlikely, possible, probable, definitely)

- Causality other than study drug (disease related, concomitant medication related, intercurrent illness, other)
- Date of onset
- Date of resolution
- Frequency of event (single, intermittent, continuous)
- Event outcome (resolved, ongoing, death)
- Action taken with ficlatuzumab (none, held, dose reduced, discontinued, medication given)
- Action taken with cetuximab (none, held, dose reduced, discontinued, medication given)

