 - Disease persistence or recurrence within 6 months of completing definitive radiotherapy for locally advanced disease, where platinum chemotherapy was administered as a component of induction and/or concurrent systemic treatment.
 - Disease progression during, or within 6 months, of treatment with platinum chemotherapy (e.g., carboplatin or cisplatin) in the recurrent and/or metastatic setting.

 The patient is not an acceptable candidate for platinum chemotherapy due to medical comorbidities, in the judgment of the local investigator.

Note: Prior platinum exposure may have occurred in any line of therapy (first line, second line, etc.) and is not required to be the most recent therapy received.

 Patients must have prior exposure to an anti-PD1 or anti-PDL1 mAb, if eligible for immunotherapy in the judgment of the local investigator.

Note: Prior exposure to investigational immunotherapies, including anti-CTLA4, anti-OX40, anti-CD40, anti-CD27, anti-TNFR antibodies or other investigational immunotherapies, is acceptable.

- Patients must have Eastern Cooperative Oncology Group (ECOG) Performance Status 0-1 at time of informed consent (see Appendix B).
- Patients must be age ≥ 18 years.
- Patients must consent to a research biopsy of tumor tissue at baseline, for conduct of
 correlative studies. In cases where a fresh biopsy is not feasible (i.e., if an accessible
 tumor site cannot be biopsied with acceptable clinical risk), archival tissue may be
 submitted instead, after discussion with and approval by the Sponsor-Investigator.
- Patients must have measurable disease per RECIST criteria, version 1.1 (see Section 6) per scan within 28 days prior to registration.
- Patients must have adequate electrolytes, liver, renal, and hematology function as defined below within 28 days of registration:
 - o Absolute neutrophil count (ANC) ≥ 1500/mm³
 - Platelet count (PLT) \geq 75,000/mm³
 - o Creatinine clearance ≥ 30 mL/min per estimated by the Cockraft-Gault formula:
 - Calculated Creatinine Clearance = [(140-age) X (actual body weight in kg) X (0.85 if female)]/(72 X serum creatinine)
 - o Total bilirubin ≤ 1.5 times upper-limit of normal (ULN)
 - AST (aspartate aminotransferase) ≤ 3 times ULN
 - ALT (alanine aminotransferase) ≤ 3 times ULN
 - Magnesium ≥ 1.2 mg/dL or 0.5 mmol/L*
 - Corrected Calcium ≥ 8.0 mg/dL or 2.0 mmol/L*
 - Potassium ≥ 3.0 mmol/L*
 - Serum albumin \geq 25 g/L (\geq 2.5 g/dL)

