(***Note:** Patients may be supplemented to achieve acceptable electrolyte values.)

- Patients must sign written informed consent prior to beginning study screening procedures. Patients must have the ability to understand and the willingness to sign a written informed consent document.
- Women of child-bearing potential (WOCBP) must agree to have a pregnancy test within 14 days prior to registration and a repeated test within 3 days of the first dose of ficlatuzumab.
- Patients must agree to use highly effective contraceptive measures while on study and for 60 days after the last dose of study drug. This includes: Men of reproductive potential AND women of childbearing potential.
 - o Effective birth control includes (a) intrauterine device (IUD) plus one barrier method; or (b) 2 barrier methods. Effective barrier methods are male or female condoms, diaphragms, and spermicides (creams or gels that contain a chemical to kill sperm).

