8.1 Screening/Pre-treatment evaluations

NOTE: All baseline evaluations should be performed as closely as possible to the beginning of treatment but must be performed within 28 days prior to registration unless otherwise indicated.

Written informed consent (prior to screening procedures)

- History and physical examination, including vital signs, weight, height, and ECOG performance status determination
- Documentation of medications subject is currently taking
- Complete blood count, including platelets, and differential
- Blood chemistry studies:
 - o BUN, creatinine, electrolytes (K⁺, Na⁺, Cl⁻, CO₂), glucose, calcium, magnesium
 - Note: Patients may be supplemented to achieve acceptable electrolyte values
- Liver function tests:
 - Total protein, albumin, total bilirubin, AST (SGOT), ALT (SGPT), and alkaline phosphatase
- Documentation of calculation of corrected calcium for eligibility criterion
- For women of child bearing potential: Urine pregnancy test within 14 days prior to registration to rule out pregnancy. (Note, negative pregnancy test must be confirmed again within 3 days prior to first study treatment.)
- Baseline tumor measurements within 28 days prior to registration.
- For oropharyngeal cases and unknown primary: HPV status (p16) status must be known or established and recorded at baseline (randomization is stratified by HPV status and documentation must be sent with the registration; see Section 4).
- Tobacco history assessment form (See Appendix D) (may be performed at screening or prior to study treatment on day 1; the assessment can be performed by method other than in-person, if needed, and the method used must be documented)
- Quality of life assessment (FACT-H&N Symptom Index) (may be performed at screening or prior to study treatment on day 1; the assessment can be performed by method other than in-person, if needed, and the method used must be documented)
- Research blood samples for correlative studies (may be performed at screening or prior to study treatment on day 1)
- Research biopsy of tumor tissue before first study drug administration (See Section
 9.2 for more information.)
- Confirm archived tumor specimens prior to cetuximab exposure are available for correlative research as outlined in Section 9.1. (Note: This is not an eligibility requirement and subjects can be randomized without this confirmation.)

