9.2 Research biopsy

All patients will be evaluated for a research biopsy at the time of enrollment. The biopsy is to be done prior to initiation of protocol treatment. Biopsies of primary tumor, accessible metastatic tumor, cutaneous lesion, or lymph node can occur in the outpatient office of the head and neck surgeon, with local anesthetic per standard of care. Biopsies of lymph nodes requiring imaging

guidance or distant metastases will occur under the care of an interventional radiologist, with ultrasound or CT guidance and local anesthetic per standard of care.

Omission of the research biopsy is allowed if performing the biopsy is not safe and/or feasible, and/or would present unacceptable clinical risk. Contact the Sponsor-Investigator for approval to omit the research biopsy. If the research biopsy is omitted, archived tumor tissue should be collected to substitute for the lack of baseline tissue. The archived tissue substituted for the Research Biopsy should be the **most recent** biopsy available and the corresponding pathology report must be obtained. (Substitution of archived tumor tissue for the research biopsy is independent of the archived tissue submission described above in Section 9.1.)

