12.3 Reporting of Serious Adverse Events

All Serious Adverse Events as defined in Section 12.1 will be collected starting Cycle 1, Day 1 and must be reported to the Sponsor. SAEs will be followed per the details indicated in protocol Section 8.5.1. SAEs must be reported to the IRB of Record per local procedure.

Regardless of attribution, SAEs must be reported to the sponsor and the UACC DSMB within 24 hours of notification of the event. SAEs will also be copied to the Aveo pharmacovigilance entity, Parexel. The FiclaYCetux Serious Adverse Event Report Form must be used to report SAEs and redacted, relevant medical records must be attached when available. Follow-up information that describes an increase in severity or risk must be submitted within 24 hours of notification of the information. Follow-up SAE reports must also be reported within 24 hours of notification of updated information related to the event.

The Sponsor, UACC DSMB, and/or the Aveo pharmacovigilance entity, Parexel, may contact site personnel with queries to ensure all necessary information is obtained.

SAEs must be recorded in the OnCore "SAEs" tab.

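### Complications of the required research biopsy that start before Cycle 1 Day 1 fall outside AE and SAE collection

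*Combined protocol and SAP*

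**What the plan says.** Two rules set the start of safety collection. Section 12.2 says that AEs "will be collected starting on Cycle 1, Day 1". Section 12.3 says that SAEs "will be collected starting Cycle 1, Day 1 and must be reported to the Sponsor".

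The biopsy comes earlier. Section 3.1 makes consent to it an entry condition: "Patients must consent to a research biopsy of tumor tissue at baseline". Section 9.2 fixes the timing: "The biopsy is to be done prior to initiation of protocol treatment". Section 8.1 lists it among the screening and pre-treatment evaluations: "Research biopsy of tumor tissue before first study drug administration". Consent is already in place by then, since section 3.1 also states: "Patients must sign written informed consent prior to beginning study screening procedures".

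The biopsy is not absolute. Section 9.2 provides: "Omission of the research biopsy is allowed if performing the biopsy is not safe and/or feasible". This needs Sponsor-Investigator approval, and archived tissue is then substituted.

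**The concern.** The biopsy is an invasive procedure done for correlative research. Section 9.2 allows image-guided sampling of lymph nodes and distant metastases, and section 9.2.1 asks for at least two 1-cm cores. Sections 3.1 and 3.2 admit platelet counts down to 75,000/mm³ and patients stable on anticoagulation after an earlier venous clot, so bleeding is a realistic complication.

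The study adds this risk, and its subjects have already consented, yet no AE or SAE rule is in force when the procedure is done. The DSMB's six-monthly review under section 11.4 covers AEs, SAEs and deviations. Biopsy events that start before dosing would not enter the AE and SAE part of that review. The stake is safety oversight and complete reporting of research-related harm, not efficacy.

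**Working it through.** The plan gives no figure to reproduce. The main check sets the provisions side by side.

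**Order of events**

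1. Written consent (3.1).
2. Screening evaluations. The biopsy is listed here (8.1; Appendix C).
3. Registration and randomization (8.2). The text requires the biopsy only before first dose, so it could fall on either side of this step.
4. Cycle 1 Day 1: first dose, and the start of AE and SAE collection (12.2, 12.3).

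**Does any other provision cover the time from biopsy to Cycle 1 Day 1?**

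| Place | What it does | Closes the gap? |
|---|---|---|
| 12.1 | Defines an AE by reference to use of a drug; the SAE definition builds on it | No. A pre-dose procedural event does not clearly qualify |
| 12.2, causality field | Lists disease, concomitant medication, intercurrent illness and other | No study-procedure option |
| 12.3 | SAEs are reportable whatever their attribution | Only inside the Cycle 1 Day 1 window |
| 10.4.1 | Toxicity evaluability starts at first ficlatuzumab | No |
| 9.2, 9.2.1 | Biopsy indication, timing and method | No rule on complications |
| Appendix C | Biopsy marked under screening only; AE row blank there. Research blood and the questionnaires carry a footnote allowing Cycle 1 Day 1; the biopsy does not | No |
| 11.4 | Identified safety issues go to the IRB, DSMB or another body | Escalation only: no collection duty, form, timeline or start date |

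Nothing opens an earlier window. A subject who is biopsied and never dosed has no Cycle 1 Day 1, so no window ever opens. Section 10.3 accrues 74 to obtain 66 eligible subjects, so 74 − 66 = 8 are allowed for ineligibility or drop-out. How many of those would be biopsied but undosed is not stated.

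**Scale, on assumed rates**

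The documents give no biopsy complication rate. Let p be an assumed serious complication rate, and take at most one biopsy for each of the 74 subjects to be accrued. Expected events = 74 × p.

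- p = 1%: 74 × 0.01 = 0.74
- p = 2%: 74 × 0.02 = 1.48
- p = 5%: 74 × 0.05 = 3.70

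If q is the share with onset before Cycle 1 Day 1, the number missed is 74 × p × q. The documents do not give q. Across q = 0 to 1 and p up to 5%, the number missed runs from 0 to 3.7. Approved omissions of the biopsy lower it further.

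**The case against.** Starting collection at first dose is a coherent choice. It matches a drug-based AE definition and toxicity evaluability from first ficlatuzumab, and no endpoint result depends on it. The biopsy is limited to methods judged safe in an outpatient setting under local anesthesia and may be omitted where risk is unacceptable. An active systemic infection needing systemic treatment in the 7 days before first dose is an exclusion, so a serious biopsy infection would probably be noticed. The Lab Manual and the site monitoring plans are not in hand and may address procedural events.

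These points limit the finding without removing it. Noticing an infection at an eligibility check is not the same as collecting and reporting it. The method limits lower the event rate but do not supply a reporting rule. A first-dose start for drug toxicity can stay in place alongside an earlier start for procedure events.

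A reader might infer more than the text supports:

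- **That biopsy complications are never captured and the DSMB sees none.** Complications with onset on or after Cycle 1 Day 1 are in the window, where grade 3 or higher AEs and all SAEs are taken regardless of cause. The start point is a calendar day, so a biopsy on Cycle 1 Day 1 before dosing, which the text does not expressly exclude, would also be covered. Section 11.4 leaves an escalation route, though a loose one.
- **That there is a 52%, 78% or 98% chance of an unrecorded serious event.** For p = 1%, 2% and 5%, 1 − (1 − p)^74 does give those values, but they are chances that at least one event occurs. Reading them as chances of a missed event further assumes that all 74 subjects are biopsied, that every event starts before dosing and that no other route works.

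**Conclusion.** The gap is real but limited in extent. If the stated rules are followed exactly, research biopsy complications with onset before Cycle 1 Day 1 are not collected or reported as AEs or SAEs, and subjects biopsied but never dosed are outside collection altogether.

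Its size cannot be estimated from the documents. The 0.7 to 3.7 events at assumed rates of 1% to 5% are an illustration, and only the pre-dose share of them would be missed. The conclusion about the rule itself needs no rate; it rests on the wording and on the assumption that no companion document sets an earlier window. PFS, sample size and the futility rule are unaffected.

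Timing limits the practical gain. The last ficlatuzumab administration is set for no later than March 31, 2021, and this text is version 10 of May 2023. An amendment now could not prospectively capture biopsies already done, although the flaw in the written plan remains.

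**What to change.** - **12.2 and 12.3:** collect and report AEs and SAEs related to the research biopsy from the procedure, or from signed consent, including in subjects who are never dosed. Keep Cycle 1 Day 1 as the start for all other AEs.
- **12.1:** extend the AE definition to study-procedure events. Without this, a pre-dose event still may not qualify and the first change has little effect.
- **Appendix C:** add an AE mark in the screening column.
- **Causality field in 12.2:** add a study-procedure option.
- **Reporting:** tabulate biopsy events separately from drug toxicity, so that the toxicity-evaluable population in 10.4.1 is unchanged.
- **Subjects already biopsied:** query source records for biopsy complications, and state the collection window in the safety report.

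The cost is an amendment, a few extra entries and one round of source queries. No treatment, endpoint or efficacy analysis changes.

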1.6.3 Ficlatuzumab Safety Experience

Refer to the Aveo Pharmaceuticals Investigator Brochure for the most up-to-date information.

Data from the first-in-human dose-escalation study (Study P05538) in 41 subjects diagnosed with relapsed or refractory solid tumors or lymphoma that was metastatic or unresectable, or symptomatic relapsed or refractory multiple myeloma showed ficialtuzumab to be well-tolerated as monotherapy at the 4 dose levels tested (2, 5, 10 or 20 mg/kg) and in combination with erlotinib (20 mg/kg ficialtuzumab and 150 mg/day erlotinib). The maximum administered dose of 20 mg/kg intravenous (IV) ficialtuzumab every 2 weeks as monotherapy and in combination with erlotinib (150 mg/day) was determined to be the RP2D.

There were no DLTs observed with single-agent ficlatuzumab. One subject in the ficlatuzumab plus erlotinib combination cohort experienced a Grade 3 mucositis which the investigator determined was possibly related to ficlatuzumab and related to erlotinib. The most common treatment-emergent adverse events (TEAEs) were fatigue (18 subjects, 44%), peripheral edema (13 subjects, 32%), hypokalemia (11 subjects, 27%), and nausea (10 subjects, 24%). The most frequently reported related TEAEs were fatigue (12 subjects [29%]; 9 subjects monotherapy [22%], 3 subjects erlotinib combination [7%]); peripheral edema (6 subjects [15%]; 5 subjects monotherapy [12%], 1 subjects erlotinib combination [2%])); headache (5 subjects [12%]; 4 subjects monotherapy [10%], 1 subjects erlotinib combination [2%]), pruritus (5 subjects [12%]; 3 subjects monotherapy [7%], 2 subjects erlotinib combination [5%]), and rash maculo-papular (5 subjects [12%]; 5 subjects erlotinib combination [12%]).

Serious adverse events (SAEs) considered at least possibly related to ficlatuzumab included Grade 1 blindness transient, Grade 4 hyperkalemia, and Grade 1 hypokalemia, one case each.

Data from a Phase 1 pharmacodynamic study (Study P05670) in 19 subjects with advanced solid tumors and liver metastases showed ficlatuzumab to be well-tolerated as monotherapy at the 2 to 20 mg/kg dose range tested. There were no DLTs in this study. The most frequently reported TEAEs were asthenia, peripheral edema, and hepatic pain (each reported by 6 subjects [32%]), and cough (5 subjects [26%]). The only related adverse event (AE) was pyrexia, which occurred in 1 subject in the 2 mg/kg treatment group (5%). There were no SAEs considered at least possibly related to ficlatuzumab.

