10.4.1 Toxicity

Patients will be evaluable for toxicity from the time of their first treatment with ficlatuzumab. The proportion of AEs will be reported in accordance with NCI CTCAE v.4.0 grading criteria.

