10.6 Statistical Analysis Plan

Progression-free and overall survival will be estimated for each arm using a Kaplan-Meier curve. Toxicities and the response rate will be tabulated and reported with 95% exact confidence intervals. The relationship between progression-free survival and the candidate biomarkers will be assessed using Cox proportional hazards models. The relationship with clinical response will be assessed using logistic regression models.

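### Toxicity proportions with exact intervals are planned for all grades and terms, but section 12.2 enters Grade 1-2 events selectively outside five listed categories

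*Combined protocol and SAP*

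**What the plan says.** Describing toxicity is a secondary objective (section 2.2). Section 10.4.1 says: "The proportion of AEs will be reported in accordance with NCI CTCAE v.4.0 grading criteria". Section 10.6 adds: "Toxicities and the response rate will be tabulated and reported with 95% exact confidence intervals". Neither section sets a minimum grade, limits the terms, or names the data source.

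Section 12.2 sets the entry rule: "Only AEs meeting one of the following criteria will be entered into the OnCore CRM study database". The criteria are:

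- "Any AE that is Grade 3 or higher, regardless of relationship to the study drug"
- events that lead to an SAE submission
- "Any intolerable (per the opinion of the treating investigator) Grade 2 AE"
- events, whatever their severity, that caused the dose of either drug to be lowered
- Grade 2 laboratory findings or vital signs, if judged clinically significant
- any grade of rash, diarrhea, peripheral edema, head/face/neck edema or hypoalbuminemia

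Just before this list, section 12.2 also places AE recording on the OnCore AE form and requires all AEs from Cycle 1, Day 1 to be recorded. Section 11.3 has case report forms, AE forms included, completed in OnCore. No other AE database is named. Section 8.5.1 adds a limit after treatment: in the 60 days after the last dose, only new drug-related AEs and pregnancy need documenting, and AE collection stops when a new antineoplastic therapy starts.

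**The concern.** Outside the five categories, a Grade 1 event reaches the database only through an SAE or a dose reduction. A Grade 2 event needs one of those, or an investigator's judgement that it is intolerable or, for laboratory and vital sign values, clinically significant. The low-grade rows for these terms therefore count a selected subset of events over a denominator of all treated patients. An exact binomial interval allows for sampling error only, not for events that were never entered.

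The selection also rests on opinion in an open-label trial (section 10.1), so the entered share may differ by site and by arm. At stake is how far the toxicity description can be trusted. A reader could set these low-grade rates beside the all-grade rates in section 1.6.3 and conclude that the drug is better tolerated here than before.

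**Working it through.** The plan gives no expected AE rate for this trial, so there is no planned figure to reproduce. The check sets the entry rule against the plan's own prior data.

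**1. Expected terms (Table 1, section 1.6.3).** Of 18 terms, 4 are entered at every grade: diarrhea, peripheral edema, hypoalbuminemia and rash. The other 18 − 4 = 14 are not; they include fatigue, nausea, vomiting, headache, pruritus, hypokalemia and hypomagnesemia.

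**2. First-in-human study (section 1.6.3, 41 subjects).** The four most common events reproduce as stated: fatigue 18/41 = 43.9%, peripheral edema 13/41 = 31.7%, hypokalemia 11/41 = 26.8%, nausea 10/41 = 24.4%. Only peripheral edema is on the any-grade list.

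**3. Dose-reduction route (Table 4B).** For fatigue, nausea/vomiting, low potassium or magnesium, pruritus and paronychia, the table specifies reductions only at Grade 3 or higher. This route therefore brings in few of their Grade 1-2 events.

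**4. Share that could be left out (Table 2, ficlatuzumab plus gefitinib, n = 90).**
- All grades: 42 + 24 + 34 + 17 + 15 + 18 + 11 = 161
- Grade 3: 0 + 1 + 2 + 0 + 2 + 2 + 0 = 7
- Below Grade 3, assuming no Grade 4-5 events (none are shown): 161 − 7 = 154
- Entered at any grade: peripheral edema 34 − 2 = 32, hypoalbuminemia 18 − 2 = 16; total 48
- Left out: at most (154 − 48)/154 = 106/154 = 69%
- If acne (24 − 1 = 23) and eczema (15 − 2 = 13) are entered as rash: at most (154 − 48 − 36)/154 = 70/154 = 45%

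These are upper limits for these terms, since some events would enter by the other routes.

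**5. One term with no Grade 3 cases.** In the same arm, paronychia was 42/90 = 46.7% (exact 95% CI 36.1-57.5%) at all grades. Through the Grade 3 criterion alone it would show 0/90 (0-4.0%). Intolerable Grade 2 cases would raise that figure.

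**6. Illustration at 33 patients per arm (section 10.3).** Let p be the true any-grade rate and q the share of affected patients whose event meets an entry criterion. The tabulated rate is then about p × q. The documents do not give q, so a range is assumed. For x cases in n, the Clopper-Pearson limits are the 0.025 quantile of Beta(x, n − x + 1) and the 0.975 quantile of Beta(x + 1, n − x).

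| Fatigue, p near 43.9% | Tabulated | Exact 95% CI |
|---|---|---|
| All entered | 14/33 = 42.4% | 25.5-60.8% |
| q = 50% | 7/33 = 21.2% | 9.0-38.9% |
| q = 25% | 4/33 = 12.1% | 3.4-28.2% |
| q = 10% | 1/33 = 3.0% | 0.1-15.8% |
| q = 0% | 0/33 = 0% | 0-10.6% |

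For hypokalemia (26.8%) and nausea (24.4%), q = 50% gives about 4/33, with interval 3.4-28.2%, which still contains the true rate.

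**The case against.** The strongest reply is that the plan never promises what would go wrong. No any-grade table is specified, nor a Grade 1-2 row for every term, and OnCore is not named as the source of the tables. Section 12.2 also requires all AEs to be recorded. An analyst who respects the entry rule could produce sound tables.

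The any-grade list also looks aimed at expected signals. Peripheral edema (38% against 4%) and hypoalbuminemia (20% against 3%) are two of the three largest between-arm differences in Table 2, and both are entered at every grade. Limiting low-grade data entry is a fair choice, the objective is descriptive in a non-comparative design, and the futility rule in section 10.7 does not use AE data.

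Much of this stands. It makes the bias conditional on tabulating from OnCore and keeps the stakes modest. It does not remove the point. Proportions by grade with no floor naturally include Grade 1-2 rows, and the documents describe no other database to fill them. The requirement to record all AEs either contradicts the entry rule or refers to source records only; the text does not say which.

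**Conclusion.** The point holds conditionally. Tabulated from OnCore as sections 10.4.1 and 10.6 are worded, Grade 1-2 and any any-grade proportions for terms outside the five categories will be biased low, and the exact intervals will not reflect that selection. The size depends on the share of events that qualify for entry, which the documents do not give; the fatigue figures above are illustrations over an assumed range.

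A reader might infer three stronger things that the documents do not support:

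- **Most Grade 1-2 events are lost.** Table 2 gives an upper limit of 45% or 69%, depending on how skin terms are coded, and covers only terms chosen for their between-arm difference.
- **Common ficlatuzumab toxicities in general are understated.** Rash, diarrhea, both edema categories and hypoalbuminemia are entered at every grade, and Grade 3 or higher rates are untouched by this filter for every term.
- **The intervals will miss the true rate.** That depends on the term and the entered share. At 50% entry, the fatigue interval misses while the hypokalemia and nausea intervals do not.

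This is a minor point: a reporting improvement to a secondary, descriptive output.

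**What to change.** - **Section 12.2:** reconcile the requirement to record all AEs with the restricted entry list, and say which applies to source records and which to the database.
- **Sections 10.4.1 and 10.6:** restrict incidence proportions and exact intervals to Grade 3 or higher for all terms and any grade for the five categories, during the on-treatment period.
- **Other Grade 1-2 events:** show them as counts only, labelled as selectively collected (intolerable, clinically significant, serious or dose-reducing). This keeps the information without presenting it as incidence.
- **Footnote:** cite the section 12.2 entry rule and the section 8.5.1 post-treatment limit to new related AEs, because unrelated events after the last dose can be missed even at Grade 3 or in a listed category.

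The cost is protocol and table-shell wording, with no new data. Section 5.1 ends ficlatuzumab dosing by March 31, 2021 and this version is dated 05/23/2023, so a change in reporting is also the practical remedy.
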